INVESTIGATOR'S ABBREVIATED PROTOCOL

1. TITLE: Prasugrel for prevention of early saphenous vein graft thrombosis

2. PRINCIPAL INVESTIGATOR: [name], PhD

CO-INVESTIGATOR: [name]

KEY MEMBERS: [name]

[name]

[name]

[name]

[name]

[name]

[name]

[name]

3. SPONSOR OF THE STUDY: VA Merit, VA OR&D

4. IND/ IDE: Not Applicable

5. PURPOSE OF THE STUDY, INCLUDING HYPOTHESIS TO BE TESTED:

Aortocoronary saphenous vein graft failure is common and is associated with high morbidity and mortality. Thrombus formation plays a critical role in early saphenous vein graft occlusion and may predispose to subsequent atherosclerosis formation. Optical coherence tomography is a novel, high-resolution, intravascular imaging technique that can reliably identify thrombus. Based on the findings of earlier VA Cooperative Studies, aspirin significantly reduces the incidence of early saphenous vein graft failure and is currently used in nearly all patients undergoing coronary bypass graft surgery. Administration of clopidogrel for improving early saphenous vein graft patency has provided conflicting results in small randomized studies. Prasugrel is a novel thienopyridine that provides more rapid, consistent, and intense platelet inhibition than clopidogrel. However, in patients who undergo coronary artery bypass graft surgery, it remains unknown whether prasugrel may decrease thrombus formation in saphenous vein grafts during the first postoperative year, and whether this will result in less saphenous vein graft wall thickening, less lipid deposition in the saphenous vein graft wall and fewer clinical events without increasing the risk for severe bleeding.

We hypothesize that in patients undergoing clinically-indicated coronary artery bypass graft surgery, administration of prasugrel starting at dismissal from the index coronary bypass graft surgery hospitalization will result in lower prevalence of thrombus formation in a target SVG, as assessed by optical coherence tomography performed 12 months post surgery compared to placebo, with similar incidence of major bleeding.

6. BACKGROUND AND RESULTS OF PREVIOUS RELATED RESEARCH:

Saphenous vein graft failure

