Approximately 120 patients will be randomized into this study at the Dallas VA Medical Center.

10. JUSTIFICATION FOR THE USE OF SPECIAL SUBJECT POPULATIONS:

Not applicable.

11. STUDY DESIGN:

The primary efficacy objective is to compare the prevalence of SVG thrombus as detected by optical coherence tomography of a target SVG between patients receiving prasugrel vs. placebo. We hypothesize that prasugrel will be superior to placebo in reducing the prevalence of SVG thrombus at 12-month follow-up OCT imaging.

The primary safety endpoint is the incidence of severe bleeding as defined using the GUSTO study criteria.⁶⁷ We hypothesize that patients receiving prasugrel will have similar incidence of severe bleeding compared to patients receiving placebo during the 12-month study period.

The secondary endpoints will be: (1) incidence of angiographic SVG failure (defined as $\geq 75\%$ SVG diameter stenosis in at least one SVG); the total and normalized total SVG atheroma volume within at least 40 mm of the target SVG, as assessed by intravascular ultrasonography; the lipid core burden index of the target SVG, as assessed by near-infrared intracoronary spectroscopy; and (2) the incidence of major adverse cardiac events and moderate bleeding during the 12-month study period.

The proposed study is a phase 3, single-center, randomized, double-blind, controlled, parallel-group study of prasugrel vs. matching placebo in patients with recent CABG, starting at the time of hospital dismissal from CABG (Figure 13). All patients will be receiving aspirin, as per standard current practice.

[figure not shown]

Figure 13: Flowchart of the proposed study design.

CABG = coronary artery bypass graft surgery; OCT = optical coherence tomography; IVUS = intravascular ultrasound; NIRS = near-infrared spectroscopy; R = randomization; m = month; FU = follow-up.

12. DESCRIPTION OF PROCEDURES TO BE PERFORMED:

The study design will be explained to the patients and if they agree to participate they will be asked to sign an informed consent form and they will receive a copy of the consent form. They will subsequently be randomized to prasugrel or placebo, as described below.

Randomization and Treatment

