Randomization will be performed based on computer-generated random numbers, and will be blocked with block sizes of 4-10, varying randomly. Subjects will be assigned on a 1:1 basis to prasugrel (Effient®, Daiichi Sankyo and Eli Lilly) at a dose of 10 mg daily or matching placebo. The patients and study coordinators will be blinded to the study medication. Angiographic, OCT, IVUS, NIRS and angiographic analyses will also be done blinded to study-arm allocation. Breaking the blind will be possible for any patient who develops a complication or whose clinical care requires knowledge of the study group allocation.

Patients randomized to the treatment arm will receive prasugrel at a dose of 10 mg daily. Patients randomized to placebo will receive one placebo tablet. To minimize the potential for side effects during the study period patients with an increased risk of bleeding [need for warfarin or oral Xa inhibitor or thrombin inhibitor administration, recent (within 30 days) major bleed, known bleeding diathesis or coagulation disorder], will be excluded from the present study.

To minimize the possibility of study medication discontinuation, adherence with the study medication will be assessed during every follow-up visit. Patients will be asked to return all unused medications and study containers. The number of tables issued minus the number of tablets returned will be used to calculate the number of tablets taken. From this information compliance will be calculated as: (number of capsules dispensed – number of capsules returned) / (number of days between visits x number of tablets per daily dose). Patients with <80% compliance with the study medication will be counseled on the importance of taking their medications.

Catheterization, OCT, IVUS, and NIRS

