	0	1m +/- 5 days	3m +/- 10 days (phone FU)	6m +/- 10 days	9m +/- 10 days (phone FU)	12m +/- 30 days	
Inclusion/Exclusion criteria reviewed	X						
Informed consent	X						
Medical history	X	X	X	X	X	X	X
Physical examination/ Vital Signs	X	X		X		X	
Medication adherence		X	X	X	X	X	
Electrocardiogram	X					X	
SVG angiography, OCT, IVUS and NIRS						X	

FU=follow-up; SVG=saphenous vein graft; IVUS=intravascular ultrasonography; NIRS = near-infrared spectroscopy; OCT = optical coherence tomography

13. ANTICIPATED DATA AND DATA ANALYSIS:

Expected treatment effect

A recent study demonstrated the presence of thrombus in 25% of SVGs examined early post CABG.⁴⁷ Given the potent antiplatelet effect of prasugrel, we anticipate 80% reduction in the prevalence of thrombus in SVGs, as assessed by OCT.

Sample size calculation

Assuming that thrombus will be detected by OCT in 25% of patients in the placebo group vs. 5% of patients in the prasugrel group (80% relative reduction), the sample size required to detect the specified difference with 80% power and a 2-sided α

level of .05 is 48 patients per group, which was increased to 60 patients to allow for 20% dropout.

Assuming 48 patients are evaluable in each group, the power of the study assuming a prevalence of thrombus by OCT in the control arm of 20%, 25%, and 30% will be 67%, 80%, and 89%, respectively.

Enrolling 40 patients per year for three consecutive years will require enrollment of 25 % of the eligible patients at our institution. Enrollment rate in the SOS trial which also required angiographic and IVUS follow-up⁶² was 56%, suggesting that enrollment of the projected number of patients is feasible in our setting.

Statistical Analysis of primary endpoints

All endpoints (primary and secondary) will be analyzed with an intent-to-treat approach.

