The prevalence of thrombus within the target SVG at 12-month OCT imaging (primary efficacy endpoint) will be analyzed using the Fisher's exact test. In view of the relatively small sample size of the trial, multivariable logistic regression analyses will be performed to adjust the findings for any potential differences in the baseline characteristics of the two study groups, which are known to influence the occurrence of SVG failure. Such characteristics are: patient age, prior myocardial infarction; total cholesterol and HDL-cholesterol levels; minimum graft diameter; mean arterial pressure; ejection fraction; male gender; and current smoking.⁶⁹ The significant characteristics will be incorporated in the calculation of an adjusted odds ratio representing the association between treatment and the prevalence of thrombus, along with 95% confidence intervals. Because off-pump and endoscopic SVG harvesting may be associated with higher rates of SVG failure, randomization will be stratified by (a) on vs. off pump and (b) endoscopic vs. open harvesting.

The time elapsed to the incidence of severe bleeding, defined using the GUSTO criteria⁶⁷ (primary safety endpoint) will evaluated using Kaplan-Meier survival curves and compared between the 2 study groups using the log-rank test.

Statistical Analysis of secondary endpoints:

The differences in angiographic SVG failure, in total and normalized total SVG atheroma volume and in lipid core burden index at 12-month SVG imaging will be compared between the 2 study groups using Fisher's exact test. A logistic regression model will be developed to evaluate the treatment effect on this outcome adjusting for patient age, prior myocardial infarction; total cholesterol and HDL-cholesterol levels; minimum graft diameter; mean arterial pressure; ejection fraction; male gender; and current smoking.⁶⁹

The incidence of major adverse cardiovascular events (composite of death, acute coronary syndrome, and coronary revascularization) at 12 months will be compared between the two study groups using the chi-square test. Kaplan-Meier survival curves and the log-rank test will be used to compare time-to-event of major adverse cardiac events in the two study groups.

All tests will be two-sided. The critical level for the primary and four secondary outcomes will be 0.05. No adjustments will be made for multiple secondary endpoints

14. PROVISIONS FOR MANAGING ADVERSE REACTIONS:

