For safety monitoring, any emergency adverse event resulting from participation in the study will be treated at the Dallas VA Medical Center. [name] will evaluate all adverse events and determine the appropriate course of action.

If a patient develops severe bleeding during the study period, prasugrel will be temporarily held and will be discontinued if the patient is considered to be at increased risk for recurrent bleeding. If a patient develops an indication for receiving oral anticoagulation therapy with warfarin or dabigatran during his or her participation in the study, prasugrel administration will be discontinued to minimize the risk of bleeding.

If any subjects are hospitalized for an acute coronary syndrome or undergo coronary angiography at an outside hospital, the hospitalization records will be obtained and reviewed by the clinical events committee. The Universal definition of myocardial infarction will be used for diagnosing myocardial infarction. Bleeding will be assessed with the use of the GUSTO criteria.⁶⁷ Severe bleeding will be defined as fatal bleeding, intracranial hemorrhage, or bleeding causing hemodynamic compromise requiring blood or fluid replacement, inotropes, or surgery.⁶⁷ The frequencies of moderate bleeding, defined as bleeding requiring transfusion not characterized as severe, and moderate/severe and severe bleeding will also be analyzed. Information on (surgical or percutaneous) coronary revascularization will also be collected. Data will be entered on paper-based case report forms and will be double-entered into a secure, password protected database, accessible only by study personnel. Subjects will be identified by a unique study number in the database.

Additionally a Data Safety Monitoring Board will be appointed to review the study periodically (every 12 months, or sooner if required).

15. RISK/ BENEFIT ASSESSMENT:

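### Severe bleeding is analysed by intent-to-treat only, although the hypothesis is similarity; a supportive on-treatment analysis should be pre-specified beside it

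*Combined protocol and SAP*

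**What the plan says.** - **Analysis set.** Section 13, Statistical Analysis of primary endpoints: "All endpoints (primary and secondary) will be analyzed with an intent-to-treat approach". The supplied text names no on-treatment, as-treated or per-protocol analysis.
- **Hypothesis.** Section 11: "We hypothesize that patients receiving prasugrel will have similar incidence of severe bleeding compared to patients receiving placebo during the 12-month study period". Section 5 makes this part of the overall hypothesis, less thrombus "with similar incidence of major bleeding". No margin is given.
- **Test.** Section 13 puts time to GUSTO severe bleeding on Kaplan-Meier curves, "compared between the 2 study groups using the log-rank test". No censoring rule is given for stopping study drug or starting an anticoagulant.
- **Stopping drug.** Section 14: if oral anticoagulation becomes indicated, "prasugrel administration will be discontinued to minimize the risk of bleeding". After a severe bleed, "prasugrel will be temporarily held and will be discontinued if the patient is considered to be at increased risk for recurrent bleeding".
- **Adherence.** Section 12 calculates compliance from tablet counts. The only stated use is that "Patients with <80% compliance with the study medication will be counseled".

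**The concern.** Whether intent-to-treat is the cautious choice depends on the claim. When the aim is to show a difference, off-drug time dilutes the contrast and works against the sponsor. When the aim is to show that the arms are alike, the same dilution works for the sponsor.

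The plan creates some of this time itself. A patient who develops a need for anticoagulation stops study drug but, under intent-to-treat, still counts in the assigned arm for the 12 months. Any bleed on the anticoagulant then counts too, and such bleeds can occur in either arm. Other early stops and poor adherence act in the same direction.

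At stake is the wording of the safety conclusion. A real excess on prasugrel would look somewhat smaller in the only bleeding comparison planned, and nothing pre-specified would show by how much.

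**Working it through.** **1. The plan's own figure.** The only sample size given is for thrombus, 25% vs 5%, two-sided 0.05, 80% power. With pooled variance (mean proportion 0.15):

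n = [1.96√(2×0.15×0.85) + 0.8416√(0.25×0.75 + 0.05×0.95)]² / 0.20² = 1.398²/0.04 ≈ 48.8, so 49 per group, against the stated 48. Then 48/0.80 = 60.

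The figure reproduces, but it says nothing about bleeding. The 20% is a dropout allowance in that sample size, not a rate of stopping drug.

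**2. Dilution (all inputs assumed).** Let HR be the on-drug hazard ratio, f the share of prasugrel-arm person-time off drug, and 1 the off-drug ratio. Then the intent-to-treat ratio ≈ (1 − f)×HR + f.

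| On-drug HR | f = 10% | f = 20% | f = 30% |
|---|---|---|---|
| 2.0 | 1.90 | 1.80 | 1.70 |
| 3.0 | 2.80 | 2.60 | 2.40 |

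Here f is a share of time, not of patients. If stops were spread evenly over the year, 20% of patients stopping would give f of about 10%.

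**3. Adding anticoagulated time in both arms (assumed).** Let both arms have 20% of time off drug, with 25% or 50% of that time anticoagulated at 3 times the baseline hazard. The mean off-drug hazard is then h = 0.75 + 0.25×3 = 1.5, or h = 0.5 + 0.5×3 = 2.0.

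Ratio = (0.8×HR + 0.2h)/(0.8 + 0.2h).

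- HR 2: 1.9/1.1 = 1.73, or 2.0/1.2 = 1.67.
- HR 3: 2.7/1.1 = 2.45, or 2.8/1.2 = 2.33.

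**4. Against the precision available.** Take 60 per arm and an assumed 2% control rate over 12 months.

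- HR 2, no off-drug time: expected events = 60×(0.02 + 1 − 0.98²) = 3.58. Schoenfeld power = Φ(√3.58×ln 2/2 − 1.96) ≈ 9.6%.
- 20% off drug, intent-to-treat (ratio 1.8): 60×(0.02 + 1 − 0.98^1.8) = 3.34 events, power ≈ 7.7%.
- 20% off drug, on treatment (ratio 2.0): 0.8×3.58 = 2.86 events, power ≈ 8.5%.
- Approximate 95% interval at 3.34 events: a factor of exp(1.96×2/√3.34) ≈ 8.5 either side of the estimate. The dilution is a factor of 2.0/1.8 = 1.11.
- HR 3, 20% off drug, intent-to-treat: 60×(0.02 + 1 − 0.98^2.6) = 4.27 events, interval factor exp(1.96×2/√4.27) ≈ 6.7. The dilution is 3.0/2.6 = 1.15.

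With control rates of 1–5%, HR 2 and no off-drug time, about 2–9 events are expected and power is about 7–18%. For 80% power at HR 2, 4×(1.96 + 0.8416)²/(ln 2)² gives 66 events.

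**5. Which stops matter.** Holding drug after a first severe bleed comes after the event and cannot dilute a time-to-first-event analysis. The dilution comes from stopping for anticoagulation, other stops before an event, and non-adherence.

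**The case against.** The strongest reply is that the bias is small and the proposed analysis changes little. With about four severe bleeds, both analyses will usually be non-significant, and the shift lies far inside the confidence interval. This stands, and it limits the weight of the point.

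A reader might infer from Section 11 that the hypothesis concerns patients actually taking the drug, so that intent-to-treat answers the wrong question. The documents do not support this. The efficacy objective in the same section uses the same phrase, so receiving most naturally means assigned to, and the safety sentence compares a fixed 12-month period.

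A reader might also infer that intent-to-treat is wrong for bleeding and should be confined to efficacy. It is not wrong. Confining it would remove a valid comparison and would leave moderate bleeding, a secondary endpoint, with no stated analysis set.

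Nor do the documents set a rule that a non-significant log-rank test establishes similarity. The risk lies in how the result is read.

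Three further points stand. Section 8 excludes patients who need anticoagulants at entry, and the adherence counselling is meant to limit non-adherence, so off-drug time may be small. On-treatment censoring can mislead in either direction: if patients at highest risk stop after minor warning bleeds, censoring them can also draw the arms together. Finally, this is an abbreviated protocol that refers at its end to an attached Sponsor's Protocol, which was not supplied and could contain such an analysis.

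**Conclusion.** The point holds as a modest, inexpensive improvement. In the supplied text, severe bleeding has an intent-to-treat analysis only, the hypothesis is similarity, and off-drug and shared anticoagulated time move the estimate toward that hypothesis. The direction rests on the off-drug hazards being equal in the two arms. The size rests wholly on assumed values: an on-drug ratio of 2 would show as about 1.7–1.9, and one of 3 as about 2.4–2.8, with 10–30% of prasugrel-arm time off drug.

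It would go too far to say that this dilution will decide the safety conclusion. The larger weakness is that similarity has no margin and is examined by a difference test with very few events, and an on-treatment analysis does not repair that. It is still worth fixing in advance. With so few bleeds, counting one or two as on-drug or off-drug changes the picture, and rules chosen after unblinding could be chosen to fit.

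**What to change.** Keep the intent-to-treat sentence for all endpoints. For severe bleeding, add to Section 13 a pre-specified, supportive on-treatment analysis:

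- **Population:** patients with at least one dose of study drug.
- **Time at risk:** from first dose to last dose plus a lag fixed before unblinding.
- **Censoring:** at permanent discontinuation plus that lag, or at the start of oral anticoagulation.
- **Reporting:** the hazard ratio or risk difference with 95% confidence interval from both analyses, side by side.
- **Interpretation:** bleeding is not to be described as similar on the intent-to-treat log-rank result alone.

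The cost is SAP wording and a little analysis work. Section 12 describes tablet counts between visits, and the month 3 and 9 contacts are by telephone. Dates of first dose, last dose and anticoagulant start are not described as collected, so case report form fields may be needed. Because the censoring can be informative, the new analysis supports intent-to-treat and does not replace it. The missing margin and the low event count need separate attention.

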Figure 2. Saphenous vein graft (SVG) and internal mammary artery (IMA) patency rates after CABG in VA Cooperative Studies #207/297/364.

SVG failure is critically important.

Mechanisms leading to saphenous vein graft failure

SVG failure is the result of 3 consecutive and inter-related processes: thrombosis, intimal hyperplasia, and atherosclerosis (Figure 3).^{11, 12} Immediately post CABG thrombus forms in SVGs due to endothelial disruption during harvesting and implantation. If the SVGs remain patent during this period, they develop a platelet-mediated progressive thickening of the vessel wall, which involves smooth muscle cell proliferation and extracellular matrix protein synthesis. Atherosclerosis subsequently develops on the ground of intimal hyperplasia, leading to decreased antegrade flow or eventually SVG occlusion.

[figure not shown]

Figure 3. Evolution of saphenous vein graft lesion development. After coronary artery bypass SVGs either occlude early or develop intimal thickening (panel 1), which forms the ground for moderate lesion development (panel 2). Moderate SVG lesions have high rates of progression to severe, symptom-causing lesions (panel 3), and eventually occlusion (panel 4).

SVG harvesting during CABG can cause significant injury, both at the time of removal from the leg and during SVG flushing to prepare the conduit for grafting.¹³ SVG wall injury may predispose to intraluminal platelet thrombus formation, which was observed in 68% of SVGs examined by OCT immediately post harvesting (Figure 4).¹³ Several factors may affect the severity of SVG injury, such as the mode of harvesting (endoscopic vs. open), manual high-pressure intraluminal distension, and the presence of baseline SVG disease. Lack

[figure not shown]

Figure 4. Identification of intraluminal thrombus formation in SVGs immediately after harvesting using optical coherence tomography (panel A) or by direct visualization (panel B).

of heparinization during SVG harvesting was associated with a trend for higher SVG occlusion rates one week post CABG, highlighting the risk for early SVG thrombosis.¹⁴

Several other factors are associated with decreased SVG patency, such as multiple distal SVG anastomoses¹⁵ and off-pump surgery,⁵ that is why SVGs with multiple anastomosis will be excluded from the present study; nearly all coronary bypass graft surgeries are performed on-pump at our institution.

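### Randomisation is stratified by pump use and harvest method, but the primary test and both covariate lists omit these factors, and the adjusted odds ratio has no defined covariate rule with about 14 expected events

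*Combined protocol and SAP*

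**What the plan says.** - **Stratification.** Section 13 (Statistical Analysis of primary endpoints) states that "randomization will be stratified by (a) on vs. off pump and (b) endoscopic vs. open harvesting". The reason given is a possible link of off-pump surgery and endoscopic harvesting with graft failure.
- **Primary test.** The same paragraph tests thrombus prevalence at 12 months with Fisher's exact test and mentions no strata.
- **Primary adjusted model.** Logistic regression is to adjust for "any potential differences in the baseline characteristics of the two study groups". The nine candidates are age, prior infarction, total and HDL cholesterol, and "minimum graft diameter; mean arterial pressure; ejection fraction; male gender; and current smoking". Then: "The significant characteristics will be incorporated in the calculation of an adjusted odds ratio".
- **Secondary model.** "A logistic regression model will be developed to evaluate the treatment effect on this outcome adjusting for patient age, prior myocardial infarction" and the rest of the same nine. There is no selection step here, and again neither stratification factor appears.
- **Randomisation section.** Section 12 (Randomization and Treatment) says: "Randomization will be performed based on computer-generated random numbers, and will be blocked with block sizes of 4-10, varying randomly". It does not mention strata.
- **Pump use at the site.** Section 6 (Mechanisms leading to saphenous vein graft failure) notes that "nearly all coronary bypass graft surgeries are performed on-pump at our institution".
- **Sample size.** Section 13 plans 48 evaluable patients per group, "which was increased to 60 patients to allow for 20% dropout".

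**The concern.** The plan treats pump use and harvest method as important enough to stratify on, then drops both from every stated analysis. Analysing by the factors used in the allocation is the usual counterpart of stratifying. Leaving them out forgoes whatever precision the stratification bought.

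The supportive odds ratio has a separate weakness. The selection sentence can be read as keeping covariates that are imbalanced between arms, or as keeping covariates associated with thrombus. The text supports either reading and gives no test, level or procedure. Two analysts could report different adjusted odds ratios from the same data, and under either reading chance largely decides which covariates enter. The plan offers this model as its answer to the small sample, so the result will be read as meaningful.

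At stake are power, coherence between design and analysis, and reproducibility. The validity of the primary test is not in question.

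**Working it through.** **Inputs from Section 13:** 25% versus 5% thrombus prevalence, two-sided α 0.05, 80% power, 48 evaluable and 60 randomised per group, 20% dropout, nine candidate covariates. The documents give no off-pump share, harvest split or stratum-specific rates; those below are assumptions.

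**1. The plan's own figures.** With mean prevalence 0.15, the pooled normal approximation without continuity correction is

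n = [1.96·√(2·0.15·0.85) + 0.842·√(0.25·0.75 + 0.05·0.95)]² / 0.20² = 48.8, i.e. 49 (stated 48).

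Dropout: 48/0.8 = 60. The same approximation at 48 per group with an 80% reduction gives 68.0%, 79.3% and 87.7% power at 20%, 25% and 30% prevalence (stated 67%, 80%, 89%). The plan's numbers therefore correspond closely to an uncorrected asymptotic test.

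**2. Events.** 48 × (0.25 + 0.05) = 12 + 2.4 = 14.4. Treatment plus nine covariates is 10 parameters, or 14.4/10 = 1.4 events per parameter. The chance of no event on prasugrel, which leaves the ordinary logistic odds ratio inestimable, is 0.95^48 = 8.5%.

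**3. Power of unstratified tests**, by exact enumeration at 25% versus 5%:

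| Placebo/prasugrel n | Fisher | MH, uncorrected | MH, corrected |
|---|---|---|---|
| 48/48 | 72.2% | 81.9% | 72.2% |
| 47/49 | 79.7% | 81.9% | 73.6% |
| 49/47 | 74.9% | 82.4% | 71.5% |
| 51/45 | 77.6% | 82.1% | 71.2% |
| Averaged over 20% binomial dropout from 60 per arm | 77.2% | 82.1% | 72.3% |

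(MH = Mantel-Haenszel.) Fisher's power depends on the split because the test is discrete; exactly equal arms occur in only 9.1% of cases. The averaged row is the fair comparison: 82.1 − 77.2 = 4.9 points. Averaged size at a common 15% is 3.4% for Fisher, 4.9% uncorrected and 2.3% corrected.

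**4. What stratifying by harvest method adds** (200,000 simulated trials, 20% dropout, 80% reduction; assumed placebo rates in two equal strata):

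| Stratum rates | MH, unstratified | CMH, uncorrected | CMH, corrected |
|---|---|---|---|
| 25/25 | 82.1% | 82.1% | 72.2% |
| 30/20 | 82.1% | 82.3% | 72.5% |
| 35/15 | 82.5% | 83.4% | 73.6% |
| 40/10 | 82.9% | 84.7% | 75.3% |

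Stratification adds 0.0 to 1.8 points. A continuity correction removes the whole gain over Fisher. Size of the uncorrected CMH is 4.9–5.0% at an overall null of 15–25%, and 4.0–4.1% at 5%.

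**5. Pump use.** If 2–10% of surgery is off-pump (assumed), 96 × 0.02 to 96 × 0.10 is about 2 to 10 evaluable patients. At the mean 15% prevalence that is 0.3 to 1.4 events.

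**6. Selection rule.** Nine independent noise covariates, 48 per arm, assumed threshold p<0.05, 4,000 simulated trials per reading. If the tests were independent, the chance that at least one passes would be 1 − 0.95⁹ = 37.0%.

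| | Outcome screen | Imbalance screen |
|---|---|---|
| At least one covariate enters | 39.7% | 35.7% |
| Adjusted/unadjusted odds ratio when one enters (5th–95th percentile) | 0.66–1.25 | 0.68–1.24 |
| Median odds ratio (unadjusted 0.162) | 0.159 | 0.162 |
| Truly prognostic binary factor (35% vs 15%) retained | 40% | 5% |

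The rule does not shift the typical estimate. It makes individual estimates depend on chance, and it often discards a covariate worth keeping. Trials with no events in an arm are excluded from the odds ratio rows.

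**7. Proposed supportive model.** Firth-penalised, with treatment, harvest method and one or two covariates (3,000 simulated trials, 20% dropout): power 79.9% or 79.4%; size at a 15% null 4.6% or 3.5%. Events per parameter are 14.4/3 = 4.8 or 14.4/4 = 3.6.

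**The case against.** **The omitted strata are not what costs the power.** This is right. Stratifying adds at most 1.8 points, and that needs assumed rates of 40% and 10% in two equal strata. At 35/15 with a 90:10 harvest split in either direction the gain is 0.1–0.5 points. The other 5 or so points come from replacing a conservative exact test with an asymptotic one. The case for including the strata is mainly coherence with the design.

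**Pump status hardly matters here.** Also right. With nearly all surgery on-pump it will probably be pooled, which leaves harvest method as the working factor.

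**Sections 12 and 13 do not conflict.** Stratified permuted blocks satisfy both. Section 12 is silent, so stating the strata there completes the text and does not correct a contradiction. The document is an abbreviated protocol that refers to an attached sponsor's protocol not seen here.

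**The adjusted model is only supportive, and its uncertainty dwarfs the selection effect.** With expected cells 12/36 and 2.4/45.6, the standard error of the log odds ratio is √(1/12 + 1/36 + 1/2.4 + 1/45.6) = 0.74. The 95% interval therefore runs from about 0.23 to 4.3 times the estimate, much wider than 0.66–1.25. The candidate list is also fixed in advance, and the selection criticism does not reach the secondary model. These points limit the harm but do not give the odds ratio a definition.

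**Unstratified Fisher is defensible with 14 events.** It is valid with guaranteed size, and the proposed test gives that guarantee up. An exact stratified test would keep it, but its power was not assessed here.

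**Conclusion.** The concern holds as an improvement that should be made; it is not a threat to validity. The stratification factors are absent from the primary test and from both covariate lists, and the primary adjusted odds ratio has no reproducible definition.

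Moving from Fisher to an uncorrected harvest-stratified CMH raises power at 25% versus 5% from 77.2% to between 82.1% and 84.7%. About 5 points of this come from leaving the exact test and 0.0 to 1.8 from the strata. Under the undefined selection rule, 36–40% of trials would admit at least one pure-noise covariate.

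These sizes rest on the plan's design rates and 20% dropout, assumed stratum rates and harvest split, an assumed p<0.05 threshold, and independent noise covariates. Correlated candidates, such as the two cholesterol measures, would change the selection figures. The textual findings need none of these assumptions.

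**What to change.** 1. **Primary test.** Specify a two-sided CMH test stratified by harvest method, and state explicitly that no continuity correction is used. Keep the unstratified Fisher test as a sensitivity analysis.
2. **Pump status.** Set one pooling rule for both test and model, applied to blinded counts before unblinding: include pump status only if enough off-pump patients are evaluable (for example at least 10, an illustrative figure), and otherwise pool it.
3. **Supportive model.** Replace significance-based selection with one pre-specified Firth-penalised logistic model: treatment, harvest method, pump status only under the same rule, and at most one or two named baseline covariates.
4. **Randomisation text.** State in Section 12 whether the blocks are formed within the strata named in Section 13.
5. **Clarification.** Say when minimum graft diameter is measured. Table 2 schedules graft imaging only at 12 months, so the variable could be post-randomisation; use it as a covariate only if it is measured at surgery.

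The cost is SAP wording only, provided that the strata were used at randomisation, which must be confirmed first. The downsides are asymptotic instead of exact size (4.0–5.0% in the null scenarios examined) and fewer covariates in the supportive model.
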